6.1 Description of Study Design

A pre/post-training quasi-experimental study is proposed to examine the effectiveness of the Stress Management and Resilience Training in increasing the levels of resiliency in healthcare personnel serving in the U.S. Air Force.

Intervention Group Assignment. Simple randomization will be utilized for participant assignment into the intervention delivery type (i.e. VTC group sessions or on-line SMART program). However, participants will be allowed to switch to their desired delivery type. We will track those individuals who chose to switch their randomized assignment. This will enhance our recruitment process and permit a component of randomized trial within a quasi-experiment. If in-person training becomes feasible and safe during the planned study period, in-person training will be used to supplement or replace VTC. Based on our estimation of the sample size needed and potential attrition, we will seek to enroll at least 60 participants into both the VTC and on-line training groups. We will assess the participants' level of resilience at baseline (enrollment) and at 12 weeks post SMART training. A second post-test will be attempted for participants who completed the SMART training no later than the end of February 2021 to test for longer-term changes in resilience.

DISTRIBUTION C: Distribution authorized to U.S. Government agencies and their contractors (administrative).

Other requests for, or further releases of this document, shall be referred to

[name].

Improving Resiliency in U.S. Air Force Healthcare Personnel

AFRL IRB APPROVED 1 SEPTEMBER 2020

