Variables and Measures. Baseline data will be collected from each participant prior to the delivery of the intervention. The baseline survey will include nine demographics questions to attain information for participant age, gender, marital status, race, ethnicity, previous deployment, military grade/rank, duty location, and military job duty (i.e. AFSC). Participants' names and preferred e-mail and phone contact information will be requested. This information is necessary to arrange a follow-up phone call for each participant approximately four weeks after completing the SMART training and to send follow-up surveys via the Research Electronic Data Capture System (REDCap™; see Intervention) at weeks 12 and 24 (if applicable) after participants complete SMART. The baseline and follow-up surveys will also include the Connor Davidson Resilience Scale (CD-RISC)²⁰⁻²¹, Perceived Stress Scale (PSS)²²⁻¹³, Generalized Anxiety Disorder Scale (GAD-7)²⁴, and five-item Quality of Life (QoL) measures.²⁵

Change in resilience scores on the CD-RISC will be the primary endpoint of the study; secondary endpoints include changes in PSS, GAD-7, and the five-item QoL measure. Although stress, anxiety, and QoL are not primary outcome variables in this study, a decrease in stress and anxiety and an increase in QoL have been reported in past studies by participants who completed SMART, in addition to changes in resilience. Including the PSS, GAD-7, and QoL measure will offer an additional opportunity, with minimum response burden, to compare participant outcomes from this study with outcomes reported in previous studies.

Connor Davidson Resilience Scale. The CD-RISC has been utilized to measure service member resilience in multiple studies.^{21, 26-30} The 25-item scale was developed from multiple studies of the characteristics of resilient individuals.⁶ Respondents can answer each item using a five point Likert scale ranging from not true at all (0) to true nearly all the time (4).⁶ A total CD-RISC score is calculated by summing the score of all 25 items for a total possible score of 100, with a higher score reflecting a greater level of resilience.⁶

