Initial recruitment and randomization will be completed during months 3 through 10 of the study. However, if the study team determines the need to recruit additional participants to ensure adequate statistical power, additional participants will be recruited in month 11 and 12. The study team will work with identified local points of contact to develop a schedule to assure the maximum number of participants can receive information about SMART during a variety of times. If approved by the chain of command, SMART could be completed during the participants' scheduled period of work. The study team will assure an IRB approved ombudsman will be present if informed consent is obtained in a group setting.

DISTRIBUTION C: Distribution authorized to U.S. Government agencies and their contractors (administrative).

Other requests for, or further releases of this document, shall be referred to

[name].

Improving Resiliency in U.S. Air Force Healthcare Personnel

AFRL IRB APPROVED 1 SEPTEMBER 2020

After informed consent is obtained and prior to the delivery of the intervention, a survey will be administered to collect demographic information and baseline measurements with the CD-RISC, PSS, GAD-7, and QoL measures. Participant demographic data, e-mail and phone contact information, and responses to survey items will be initially completed using a paper survey prior to the delivery of SMART and manually entered into the Research Electronic Data Capture System (REDCapTM; DHHS/NIH/NCRR #8UL1TR000041) by a study team member. If a participant prefers, they will be provided a web-link to enter the initial information directly into REDCapTM.

REDCapTM is a secure and encrypted, web-based platform licensed to and managed by the University of New Mexico Health Sciences Center Clinical and Translational Science Center (UNM HSC CTSC).³⁶ REDCapTM includes a suite of research tools for project management, survey administration, encrypted database storage and retrieval, and reporting.³⁶ REDCapTM will be utilized to administer follow-up surveys at week 12 and 24 (if applicable) after participants complete SMART. We propose to collect the 24-week follow-up survey responses in order to conduct an exploratory analysis to assess the longevity of the effect of SMART on resilience and stress.

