Study team members will verify participant data has been entered correctly. Participant e-mail and phone contact information will be used to schedule a follow-up phone call two weeks after completing the SMART training (see intervention). Participants' e-mail contact information will be used to send follow-up surveys through REDCapTM. Each survey will take approximately 10 to 15 minutes for participants to complete. If the participant does not respond to the initial REDCapTM invitation, a maximum of three e-mail reminders (one reminder per week after the initial e-mail is sent) will be sent to complete the survey.³⁷ If a participant does not complete the survey after all e-mail requests have been sent, a study team member may call the participant to verify their e-mail information and offer to assist the participant with accessing the survey. Because participants' demographic information will be associated with an individual's contact information in REDCapTM, demographic information will not be requested as part of the surveys at weeks 12 or 24. All data will be de-identified prior to exporting the data for analysis.

Data Analysis. IBM[®] SPSS[®] Statistics (version 26) and R (survey package, version 3.61) will be used for the statistical analysis. Initial analysis will include descriptive statistics, including means or medians, frequencies and percentages, as appropriate, to characterize demographic status, military grade, duty location, military occupation, and previous deployment status. Cronbach's α will be calculated for each multi-item scale.

The objectives of our analysis include testing and estimating the efficacy of the intervention by comparing pre-post intervention changes (improvements) in the outcome measurements of interest. Analyses will be reported as point estimates with 95% confidence intervals and appropriate estimates of effect size. In this analysis, both the VTC and on-line groups will be analyzed separately and scores will also be pooled together to test for overall intervention effects.

To better understand factors that can impact the intervention effects, we will conduct regression models on the pre-post intervention difference while controlling for demographic characteristics,

DISTRIBUTION C: Distribution authorized to U.S. Government agencies and their contractors (administrative). Other requests for, or further releases of this document, shall be referred to
[name].

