Improving Resiliency in U.S. Air Force Healthcare Personnel
AFRL IRB APPROVED 1 SEPTEMBER 2020

AFSC, and previous deployment. We will also take into consideration potential clustering effects among the participants from the same organizational unit using random effects (e.g. in regression models).

Changes in resilience, stress, anxiety, and QoL over time will be assessed by separately analyzing changes from baseline to week 12 and to week 24. A joint analysis of the longitudinal trend over the three time points at baseline, 12-week, and 24-week will be completed. We will also consider a joint analysis of resilience, stress, anxiety, or QOL, as well as, analysis for subscales of any specific domain of interest.

Section 7: Subject Selection

7.1 Do you plan to target a specific population for your study? Yes No

If Yes, please complete 7.2

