Participants will be made aware that the SMART course may be provided in a group setting. During any interactive portion of the course, participants may volunteer to provide information, thoughts, and feedback; however, they are not required to provide any information. All follow-up phone calls will be scheduled at a time and location of the participants' choosing. For all baseline and follow-up surveys, participants may choose which items they complete.

All data files used during the data analysis will be password protected. Any printouts from software (e.g. IBM® SPSS® Statistics) will be de-identified. Settings in REDCap™ will be enabled to ensure that only [name] will be able to identify a specific participant and their survey responses based upon a linked number assigned by REDCap™ when the surveys are completed.

Section 15: Data Sharing Plan

Collected data will be stored in the REDCap™ project database hosted by the UNM HSC CTSC Informatics behind the firewall of the HSC. Access from outside of the UNM HSC will require the use of a secure UNM HSC Net ID. [name] and other team members who are employees of the

DISTRIBUTION C: Distribution authorized to U.S. Government agencies and their contractors (administrative).

Other requests for, or further releases of this document, shall be referred to

[name].

Improving Resiliency in U.S. Air Force Healthcare Personnel
AFRL IRB APPROVED 1 SEPTEMBER 2020

UNM HSC will complete the planned data analysis. Printed study documents will be locked a filing cabinet located in [name] office.

After the study is completed, the de-identified data may be placed in a central storage location at the UNM HSC. Identifiers (i.e. name, phone and e-mail contact information) will be removed from the data and non-identifiable data could be used for future research studies or distributed to another investigator for future research studies without additional informed consent from participants. The purpose is to make study data available to other researchers.

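### The explanatory regression on the pre-post difference omits the baseline score; reporting the same model with baseline added beside the planned one is a cheap, modest improvement

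*Combined protocol and SAP*

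**What the plan says.** Section 6.1 (Data Analysis) gives the purpose of the regression as "To better understand factors that can impact the intervention effects". The model is described in one sentence: "we will conduct regression models on the pre-post intervention difference while controlling for demographic characteristics", continuing over the page with "AFSC, and previous deployment". Clustering by organisational unit may be handled with random effects.

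The nine demographic questions are enumerated under Variables and Measures in the same section. They cover personal characteristics, rank, duty location, job code and deployment; none is a scale score. Nowhere is the baseline score named as a covariate. The joint analysis over baseline, week 12 and week 24 uses baseline as a time point, not as a factor.

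The score will be available. Section 6.1 (Procedures) plans "baseline measurements with the CD-RISC, PSS, GAD-7, and QoL measures" before training. Section 14 notes that "participants may choose which items they complete", but a participant without a baseline score has no difference to model either.

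**The concern.** This is the plan's only model of what influences change, and it says nothing about where people started. CD-RISC is summed "for a total possible score of 100", and the Air Force mean that the protocol cites is already high, so the starting score limits how much some participants can gain. A model meant to find influences on response would naturally include it.

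Two things are at stake, both minor. Intervals for factors unrelated to baseline are somewhat wider than they need be. And for rank, AFSC or deployment, which are not randomised, the coefficient can depend on whether baseline is in the model. A reader shown only one version cannot see that dependence.

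**Working it through.** **Inputs.** Assumed change 7.7 with SD 8.7, 120 enrolled, 25% attrition, 45 completers per group, 90% power for 0.5 SD (section 10.1). Air Force mean 83.66, SD 11, and test-retest coefficient 0.87 (section 6.1, Connor Davidson Resilience Scale). Maximum score 100 (same place). The documents give no pre-post correlation r and no baseline gap by rank, AFSC or deployment, so both are assumptions here.

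**1. The plan's own figure.** 120 × 0.75 = 90, or 45 per group. A two-sided paired t-test at 0.05 with n = 45 and a difference of 0.5 SD has power 90.7% (noncentral t). The stated 90% reproduces, and nothing below changes it.

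**2. Room to improve.** A gain of 7.7 is impossible above 100 − 7.7 = 92.3. Under a normal curve, (92.3 − 83.66)/11 = 0.785, which leaves 21.6% above. That curve also puts 7% above 100. Distributions bounded at 100 with the same mean and SD give 24% to 25%.

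**3. Pre-post correlation.** With equal variances, var(change) = 2·SD²·(1 − r). So r = 1 − 8.7²/(2 × 11²) = 1 − 75.69/242 = 0.687. The values 0.87 (the test-retest figure) and 0.5 (assumed) serve as a range.

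**4. Precision, factor unrelated to baseline.** Baseline explains (1 − r)/2 of the variance of change, so the standard error is multiplied by √((1 + r)/2):
- r = 0.687: 0.918, about 8% smaller
- r = 0.87: 0.967, about 3% smaller
- r = 0.5: 0.866, about 13% smaller

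For one 45/45 factor, the 95% half-width is 1.987 × 8.7 × √(2/45) = 3.64 without baseline, and 1.988 × 8.7 × √(2/45) × 0.918 = 3.35 with it.

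**5. Precision, factor related to baseline.** With factor-baseline correlation ρ, the multiplier becomes √((1 + r)/2)/√(1 − ρ²). For a 45/45 factor with a stable gap g, ρ = (g/2)/√(121 + (g/2)²). At r = 0.687, a 5-point gap gives ρ = 0.222 and a 6% gain; an 8-point gap gives ρ = 0.342 and a 2% gain. The gain is gone at ρ = √((1 − r)/2) = 0.40 (0.25 at r = 0.87, 0.50 at r = 0.5).

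**6. Two models, different answers.** Take equal underlying gains, no cap, an assumed 5-point baseline gap and r = 0.687. The models differ by 5 × (1 − 0.687) = 1.57 points. The coefficient for the higher-scoring group, whose correct value is zero, is:

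| Baseline gap | Planned model | With baseline |
|---|---|---|
| Stable group difference | 0.0 | +1.6 |
| Transient | −1.6 | 0.0 |

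A simulation with 90 participants and a 5.5-point gap shows the same symmetry. At r = 0.687 the wrong model rejects 15% to 16% of the time and the right one about 5%; at r = 0.87 the wrong model rejects about 9%. With the cap at 100 and a stable 5-point gap, neither is exactly right: −0.7 planned and +1.2 adjusted at r = 0.687.

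**7. The baseline coefficient itself.** Without any cap or differential response, the slope of change on baseline is r − 1 = −0.31. With the cap it is −0.42 in simulation.

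**The case against.** The strongest reply is that the plan contains no error here. Regressing change on participant characteristics is a legitimate answer to who changed more, the description is one sentence about a subsidiary analysis, and that sentence does not say its list is exhaustive. This stands, and it is why the point is only a suggestion.

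A reader might infer that the planned model is biased and the baseline-adjusted one corrects it. The documents do not support that. For a stable group gap without the cap, the planned model is the right one and the added model is off; for a transient gap it is the reverse. Nothing in the protocol says which holds.

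A reader might also expect the added coefficient to show whether low scorers respond better. It cannot: there is no untrained group, regression to the mean alone gives a negative slope, and a linear term does not remove a ceiling.

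The clearest precision gain would be for delivery type, where "Simple randomization will be utilized for participant assignment into the intervention delivery type". But delivery type is not listed in this regression; the groups are to be analysed separately and pooled. The 3.64 to 3.35 figure is for a single two-level factor, whereas the planned model has many terms.

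The inputs are also loose. The change SD comes from a cited pilot in breast cancer survivors, the score SD from Air Force personnel. With SD 11, r = 0.87 would imply a change SD of 5.6 and r = 0.5 one of 11.0, so those rows are a range rather than alternatives consistent with 8.7. And for the 0.5 SD effect used in the power statement (0.5 × 8.7 = 4.35 points), about 14%, not 22%, would start too high to show it.

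**Conclusion.** The omission is real and the consequence small. Adding baseline would narrow intervals by roughly 3% to 13% for factors unrelated to it, and by less or nothing for related ones. For the non-randomised factors that are listed, the second model shows how far a coefficient depends on an assumption that the data cannot settle. The 1.6-point difference at an assumed 5-point gap is smaller than the half-width of about 3.5 points, so disagreement between the models is uncertainty, not evidence that one group responded differently.

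It would be wrong to infer that the primary result or the sample size is in doubt: the paired pre-post comparison does not use this model. The sizes rest on equal pre and post variances, on the cited SDs applying to this sample, and on assumed correlations and gaps. This is worth considering, at medium confidence.

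**What to change.** - Keep the planned change-score model. Report beside it the same model with the mean-centred baseline of the same scale added, for CD-RISC, PSS, GAD-7 and each of the five QoL items.
- State in advance that for rank, AFSC, deployment and the other non-randomised factors the two models answer different questions, and that disagreement will be reported as uncertainty.
- If delivery types are compared, use the baseline-adjusted model by randomised assignment, because "participants will be allowed to switch to their desired delivery type".
- Describe the baseline coefficient as descriptive only.
- As the ceiling check, report how many participants start above 92.3 and plot change against baseline, looking for pile-up at 100 rather than for a slope.

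The cost is a few lines of wording, one degree of freedom per model, one count and one plot. There is also a second column of exploratory coefficients for each of the eight outcomes at each time point modelled, and by group as well if the regressions are run that way; these should be labelled exploratory. No new data are needed and no further participant is lost.

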7.2 Equitable Subject Selection Rationale

7.3 Inclusion & Exclusion Criteria

A subject who has met all of the following criteria is eligible for participation in the study:

Participants must be active component healthcare personnel (any 4XXX Officer or Enlisted AFSC) serving in the U.S. Air Force, assigned to 88th MDG and USAFA at WPAFB, OH. Participants must be ≥ 18 years of age to participate.

A subject who meets any of the following criteria is disqualified from participation in the study:

Adults unable or unwilling to provide consent and individuals who are not yet adults will be excluded from this study. Active component Air Force service members without a healthcare AFSC will be excluded from the study.

7.4 Recruitment Plan

Study team members will work to recruit a sample of active component Air Force healthcare personnel. The 88th MDG and USAFA Commanders have provided letters of support to recruit potential participants with posted flyers, newspapers, social media, and informational e-mail announcements.

If allowed by University of New Mexico and WPAFB guidelines, study team members will travel to WPAFB to provide scheduled informational sessions and to attain participant consent. VTC informational sessions will also be scheduled and provided. For in-person recruitment sessions, all infection control practices and guidelines required by the installation will be enforced. Informational sessions will be coordinated at the 88th MDG and USAFA to occur at unit or staff meetings and open sessions in prearranged locations. The purpose of these sessions is to maximize study recruitment by providing information regarding the proposed research and answering any questions that potential participants may have. The location, number, and timing of these sessions will be designed to make information about the study accessible to service members on all shifts. On-site

DISTRIBUTION C: Distribution authorized to U.S. Government agencies and their contractors (administrative).

Other requests for, or further releases of this document, shall be referred to

[name].

Improving Resiliency in U.S. Air Force Healthcare Personnel

AFRL IRB APPROVED 1 SEPTEMBER 2020

liaisons will assure an IRB approved ombudsman will be present for all group informational sessions.

Team members will be attired in civilian clothing during these meetings. Although [name] is a Colonel in the active component Air Force and [name] is a Colonel in the Air Force Reserve, neither individual is in the chain of command of any of the potential participants. Therefore, the PI and AI cannot order a potential participant to complete the proposed study or affect any of the potential participant's careers.

7.5 Informed Consent

7.5.1 Waiver of Documentation of Consent

7.5.1.1 Indicate whether either of these apply

 Yes	The only record linking the subject and the research would be the consent document and the principal risk would be potential harm resulting from a breach of confidentiality. Each subject will be asked whether the subject wants documentation linking the subject with the research and the subject's wishes will govern.
 No	

OR

 Yes	The research presents no more than minimal risk of harm to subjects and involves no procedures for which written consent is normally required outside of the research context.
 No	

If Yes to either, this study qualifies for a Waiver of Documentation of Consent. Please use the [Abbreviated Consent template](#).

7.5.2 Consent Plan

Informed consent will be completed by a study team member after the completion of the described information sessions with individuals or groups. Any potential participant who wishes additional time to review the study information before providing consent will be able to do so. Participants will be provided with a copy of the consent document and will be informed that they may withdraw from the study at any time. Informed consent will be obtained from participants prior to baseline data collection.

